1.0 Study Summary

Study Title	Comparison of clinical and radiographic results of collared and collarless femoral stems in total hip arthroplasty
Study Design	Randomized controlled trial
Primary Objective	SA1: Prospectively assess clinical outcomes in patients undergoing primary total hip arthroplasty with a collared versus collarless femoral stem of the same design.
Secondary Objective(s)	SA2: Evaluate serial radiographs to quantify differences in subsidence between collared and collarless implant groups. SA3: Report and compare incidence rates of intraoperative and postoperative periprosthetic fractures and aseptic loosening following primary total hip arthroplasty with use of either a collared or collarless stem.
Research Intervention(s)/Investigational Agent(s)	N/A
IND/IDE #	N/A
Study Population	Adults (≥ 18 years) undergoing primary total hip arthroplasty with use of collared or collarless femoral stem.

MOD00024127

Page 2 of 18

Revised: November 12, 2025 IRB Approved

12/18/2025 - 11/3/2026

PROTOCOL TITLE: Comparison of clinical and radiographic results of collared and collarless femoral stems in total hip arthroplasty

Sample Size	100
Study Duration for individual participants	Preoperative consent to completions of postoperative followup (up to 1 year per patient)
Study Specific Abbreviations/Definitions	THA – Total Hip Arthroplasty PPF – Periprosthetic Fracture

2.0 Objectives*

SA1: Prospectively assess clinical outcomes in patients undergoing primary total hip arthroplasty with a collared versus collarless femoral stem of the same design.

SA2: Evaluate serial radiographs to quantify differences in subsidence between collared and collarless implant groups.

SA3: Report and compare incidence rates of intraoperative and postoperative periprosthetic fractures and aseptic loosening following primary total hip arthroplasty with use of either a collared or collarless stem.

Hypothesis: The addition of a collar to the same designed triple-taper primary hip stem will lead to a reduction in subsidence and incidence of perioperative and periprosthetic femur fractures.

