3.0 Background*

Total hip arthroplasty (THA) is a widely successful and common orthopedic intervention used to replace damaged hip joints with artificial components; however, femoral component-related complications such as early subsidence, aseptic loosening, and periprosthetic femoral fractures (PPFs) continue to challenge long-term outcomes. Recent attention has focused on femoral stem design modifications—particularly the addition of a collar—to enhance primary stability and reduce the risk of early failure. The rationale for collar usage lies in its theoretical ability to provide mechanical support at the calcar, thereby preventing stem migration and improving load transfer in uncemented femoral stems.

The release of the ACTIS Hip Stem (DePuy Synthes, 2018) has contributed to a resurgence in the use of collared stems, prompting renewed clinical inquiry into their comparative performance. Despite encouraging early results, the current evidence remains incomplete. Notably, most data derive from retrospective series or registry-based analyses, which are inherently subject to selection bias and inconsistent reporting standards, particularly concerning intraoperative PPFs and stem revisions. Additionally, DePuy Synthes has recently released the exact same stem without a collar for similar use in primary THA.

MOD00024127

Page 3 of 18

Revised: November 12, 2025 IRB Approved

12/18/2025 - 11/3/2026

PROTOCOL TITLE: Comparison of clinical and radiographic results of collared and collarless femoral stems in total hip arthroplasty

Recent studies suggest that collared stems may indeed reduce the incidence of PPFs. Favroul et al. observed a significantly lower 90-day PPF rate in the collared stem group (0.4%) compared to the collarless group (1.6%) in a cohort of 1,623 THAs ($p = 0.048$). Aseptic loosening, a leading cause of THA failure, may also be mitigated by the use of a collared design. In a Swiss National Joint Registry study of over 30,000 THAs, collared Corail™ stems had a significantly lower revision rate for aseptic loosening (0.47%) than collarless stems (0.73%; $p = 0.022$).

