Perhaps most compelling is the growing body of evidence linking collared stems to reduced femoral stem subsidence—an early indicator of mechanical instability and a predictor of later aseptic loosening. A randomized controlled trial using radiostereometric analysis (RSA) found that collared stems exhibited significantly less subsidence than collarless stems at two weeks postoperatively (mean difference 2.23 mm; $p = 0.023$), although the difference diminished by one year. Additional studies using non-invasive EBRA (Ein-Bild-Röntgen-Analyse) confirm that collared stems consistently demonstrate lower average subsidence over 6 to 18 months.

Despite promising preliminary data, several gaps in the literature persist. For example, intraoperative PPFs are typically treated intraoperatively and may lead to a change in the femoral component type that is utilized. Often, this is not captured in retrospective reviews or during chart assessment even with prospectively collected data. Such arguments support the necessity of a controlled, prospective study directly comparing collared and collarless stems with standardized measurement of femoral stem subsidence and documentation of associated complications such as aseptic loosening and PPF. Furthermore, the clinical significance of early migration differences observed with various imaging modalities has not been fully elucidated, nor has their correlation with long-term outcomes been firmly established.

This proposed randomized controlled trial seeks to address these gaps by comparing the clinical and radiographic outcomes of collared versus collarless femoral stems in THA, using femoral stem subsidence as the primary endpoint and incidence rates of PPF, aseptic loosening, and PROMs as key secondary endpoints. By employing standardized radiographic measurements and robust follow-up, this study will offer high-quality evidence to inform implant selection and optimize surgical outcomes. It will also contribute to the development of clinically relevant thresholds for subsidence that can serve as early predictors of implant failure.

References:

<https://doi.org/10.1016/j.jor.2024.01.013>

MOD00024127

Page 4 of 18

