17.0 Data Management* and Confidentiality

Femoral stem subsidence will be the primary outcome, measured in millimeters at 6 weeks, 6 months, and 1 year postoperatively. Differences in mean subsidence between the collared and collarless groups will be assessed using independent samples t-tests or nonparametric alternatives if assumptions of normality are not met. Incidence of PPF and aseptic loosening will be compared using chi-square tests or Fisher's exact tests. Logistic regression or Cox proportional hazards modeling will be used to adjust for covariates such as age, BMI, Dorr classification, and surgical approach if sample size allows. A sample size of 20 participants per group (40 total) provides 80% power to detect a difference of 0.4 mm in mean stem subsidence, assuming a standard deviation of 0.45 mm (based on prior RSA-based studies), with $\alpha = 0.05$. A proposed target enrollment of 100 participants is set to account for unforeseen dropouts.

All study team members will be trained in HIPAA compliance and Good Clinical Practice (GCP). Electronic data will be stored in a secure, password-protected, encrypted research database hosted on institutional servers. Subject identifiers (e.g., name, MRN) will be stored separately from study data and linked only via a unique coded identifier. Transmission of data between team members or collaborators will occur via encrypted institutional email or secure file-sharing platforms. No data will be shared externally without IRB and institutional approval.

Information Included:

- Demographic data, medical history, surgical details, implant type, radiographic images and measurements, and clinical outcomes (e.g., fracture, loosening, revision surgery).

Storage Location and Method:

- Data will be stored on secure, password-protected, encrypted institutional servers.
- Only authorized members of the research team listed on the IRB application will have access.
- The PI will oversee access and approve any data sharing requests.

18.0 Provisions to Monitor the Data to Ensure the Safety of Subjects – N/A

This proposed research study does not involve more than minimal risk to subjects, since it aligns with standard of care for THA procedures.

MOD00024127

Page 14 of 18 Revised: November 12, 2025 IRB Approved

12/18/2025 - 11/3/2026

PROTOCOL TITLE: Comparison of clinical and radiographic results of collared and collarless femoral stems in total hip arthroplasty

-

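### The section 2 hypothesis that a collar reduces fractures is put to a significance test that 100 patients cannot usefully perform; the confirmatory claim should be confined to subsidence

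*Protocol*

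**What the plan says.** Section 2.0 states one directional hypothesis with two parts: the collar "will lead to a reduction in subsidence and incidence of perioperative and periprosthetic femur fractures". Specific aim SA3 in the same section is to "Report and compare incidence rates of intraoperative and postoperative periprosthetic fractures and aseptic loosening".

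Section 17.0 gives the analysis. "Incidence of PPF and aseptic loosening will be compared using chi-square tests" or Fisher's exact tests, with no condition attached. It continues: "Logistic regression or Cox proportional hazards modeling will be used to adjust for covariates", naming BMI, age, surgical approach and Dorr classification as examples and making the modelling conditional on there being enough patients. Mean subsidence, the primary endpoint, is compared by t-test or a nonparametric alternative, without covariates.

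The only sample size calculation (sections 12.0 and 17.0) is for subsidence: 20 per group for a 0.4 mm difference with SD 0.45 mm. Enrolment is set at 100, 50 per group.

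Section 3.0 cites a "lower 90-day PPF rate in the collared stem group (0.4%) compared to the collarless group (1.6%) in a cohort of 1,623 THAs", and a registry study with revision rates for aseptic loosening of 0.47% (collared) and 0.73% (collarless). It describes fracture and loosening as key secondary endpoints. Nowhere does the protocol call their comparison descriptive or exploratory.

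**The concern.** Fracture reduction stands in the hypothesis on the same footing as subsidence and is given a significance test, yet fracture is a rare event and the trial was sized on a continuous measurement. If the test has almost no chance of reaching significance even when the collar gives the fourfold reduction in the cited cohort, a null result is nearly settled in advance. It would be reported against the trial's own stated hypothesis, and a surgeon choosing an implant could read it as showing that the two stems carry the same fracture risk.

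A second, smaller matter sits in the same paragraph of section 17.0. The adjusted models named there are for binary or time-to-event outcomes, where events will be too few to support them. The continuous primary endpoint, which could use the covariates, has no adjusted analysis.

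**Working it through.** **Reproducing the plan's own figure.** Two means, two-sided α = 0.05, power 80%: n per arm = 2 × (1.960 + 0.842)² × 0.45² / 0.4² = 19.9, so 20. This agrees with sections 12.0 and 17.0. Sidedness is not stated; one-sided would give 16, so two-sided is used below.

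**Inputs for fracture.** Rates of 0.4% and 1.6% (section 3.0); 50 per arm (section 12.0), taken as complete with no dropout.

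**Expected fractures.** 50 × 0.004 = 0.2 collared and 50 × 0.016 = 0.8 collarless, 1.0 in total. Probability of none in the trial: 0.996^50 × 0.984^50 = 0.365.

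**What the tests need, with no fracture in one arm of 50:**
- Fisher, two-sided: 5 v 0 gives p = 0.056 and 6 v 0 gives p = 0.027, so six are needed.
- Uncorrected chi-square: 3 v 0 gives p = 0.079 and 4 v 0 gives p = 0.041, so four are needed.

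**Power at 50 per arm**, summing the two binomial distributions over all significant tables, first at the cited rates and then at multiples keeping the 4:1 ratio:

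| Collared v collarless | Multiple | Expected fractures | Fisher | Uncorrected chi-square |
|---|---|---|---|---|
| 0.4% v 1.6% | 1 | 1 | 0.01% | 0.7% |
| 0.8% v 3.2% | 2 | 2 | 0.3% | 5.1% |
| 1.2% v 4.8% | 3 | 3 | 1.8% | 12% |
| 2% v 8% | 5 | 5 | 9.3% | 26% |
| 4% v 16% | 10 | 10 | 37% | 54% |

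A one-sided Fisher test at the cited rates has power 0.10%. For 80% two-sided Fisher power against 0.4%, the collarless rate would have to be about 16.5%.

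**Size needed at the cited rates**, with p̄ = 0.01: n per arm = [1.960 × √(2 × 0.01 × 0.99) + 0.842 × √(0.016 × 0.984 + 0.004 × 0.996)]² / 0.012² = 1,079. That is about 22 times the planned arm (1,079 / 50 = 21.6).

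**What a null result would exclude.** With 0 of 50 in an arm, the exact 95% upper limit is 1 − 0.025^(1/50) = 7.1%, against a cited collarless rate of 1.6%. With 0 v 0, the Newcombe interval for the difference is about −7.1 to +7.1 percentage points, against a cited difference of 1.6 − 0.4 = 1.2 points.

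**Loosening.** The cited revision rates would give 50 × (0.0047 + 0.0073) = 0.6 events. This is not a forecast for the trial: section 6.0 also counts radiolucent lines and implant migration as loosening, and the protocol gives no rate for that broader definition.

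**Adjusted models.** About one expected fracture against four named covariates cannot support a logistic or Cox model, so the condition in section 17.0 would not be met for fracture at the cited rates.

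**The case against.** Secondary endpoints are ordinarily unpowered. The protocol labels fracture and loosening secondary, sizes the trial on subsidence only, claims no power for fracture and does not say that a null result would be read as equal risk. All of that stands, and the point is not that fracture must be powered. It is that section 2.0 nevertheless makes fracture reduction part of the hypothesis and section 17.0 tests it, with nothing marking it as descriptive.

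The cited rates are also background citations, not planning figures. The fracture rate covers 90 days, whereas the trial adds intraoperative fractures and runs to one year, so its rates may be higher. Hence the range above; the conclusion survives it. Dropout, and the exclusion of severe osteoporosis in section 10.0, could push the other way.

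Some stronger readings are tempting, but the documents do not support them:
- *Loosening is also an untestable hypothesis with about 0.6 events expected.* The hypothesis does not name loosening; it enters through SA3 and the section 17.0 tests. The 0.6 rests on revision rates, narrower than the trial's definition, so the event count is uncertain.
- *The protocol commits to unfittable models.* It makes them conditional, so with about one fracture they would simply not be fitted.
- *Significance needs a 6 v 0 split.* That holds for Fisher only; uncorrected chi-square, which section 17.0 also allows, reaches p = 0.041 at 4 v 0.
- *The unadjusted t-test is an error.* It is valid under randomisation. Adjustment is a gain in precision.
- *The section 3.0 aim concerning "development of clinically relevant thresholds for subsidence that can serve as early predictors of implant failure" should be struck out.* The protocol says only that the study will contribute to this, and the present point does not depend on it.

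**Conclusion.** The concern holds for the fracture part of the hypothesis. At the cited rates the planned tests have power of 0.01% to 0.7%, and at ten times those rates 37% to 54%. The trial cannot usefully test that part, and a non-significant comparison would not be evidence of equal risk. This assumes 50 complete patients per arm, two-sided α = 0.05 and the cited fourfold ratio.

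For loosening, the firm statement is narrower: the trial is not sized for the comparison, the cited rates do not match its endpoint, and the number of events cannot be predicted from the protocol.

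The conditional models are a misplacement rather than a fault: adjustment is offered where events are too few and absent where the data could carry it. The sizing and validity of the subsidence comparison are unaffected. The change should be made because it alters what the trial may claim and costs almost nothing.

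**What to change.** - **Section 2.0:** confine the confirmatory hypothesis to subsidence.
- **SA3 and section 17.0:** restate fracture and loosening as descriptive. Report counts per arm with exact 95% confidence intervals for each rate and for the risk difference, and state that absence of a significant difference does not show equal risk.
- **Section 17.0, primary endpoint:** analyse subsidence with a linear model adjusted for prespecified baseline covariates: age, BMI, Dorr classification and site. The first three are already collected and site is known for every patient. Site is preferred to surgical approach because approach is recorded as operative data, and nothing in the protocol fixes it before allocation.

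The cost is some rewording and a standard model, with no added patients, visits or measurements. The downside is giving up a formal fracture claim, which the trial could not have supported. The precision gained from adjustment depends on how well the covariates predict subsidence, for which the protocol gives no figure.

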3.0 Background*

Total hip arthroplasty (THA) is a widely successful and common orthopedic intervention used to replace damaged hip joints with artificial components; however, femoral component-related complications such as early subsidence, aseptic loosening, and periprosthetic femoral fractures (PPFs) continue to challenge long-term outcomes. Recent attention has focused on femoral stem design modifications—particularly the addition of a collar—to enhance primary stability and reduce the risk of early failure. The rationale for collar usage lies in its theoretical ability to provide mechanical support at the calcar, thereby preventing stem migration and improving load transfer in uncemented femoral stems.

The release of the ACTIS Hip Stem (DePuy Synthes, 2018) has contributed to a resurgence in the use of collared stems, prompting renewed clinical inquiry into their comparative performance. Despite encouraging early results, the current evidence remains incomplete. Notably, most data derive from retrospective series or registry-based analyses, which are inherently subject to selection bias and inconsistent reporting standards, particularly concerning intraoperative PPFs and stem revisions. Additionally, DePuy Synthes has recently released the exact same stem without a collar for similar use in primary THA.

MOD00024127

Page 3 of 18

Revised: November 12, 2025 IRB Approved

12/18/2025 - 11/3/2026

PROTOCOL TITLE: Comparison of clinical and radiographic results of collared and collarless femoral stems in total hip arthroplasty

Recent studies suggest that collared stems may indeed reduce the incidence of PPFs. Favroul et al. observed a significantly lower 90-day PPF rate in the collared stem group (0.4%) compared to the collarless group (1.6%) in a cohort of 1,623 THAs ($p = 0.048$). Aseptic loosening, a leading cause of THA failure, may also be mitigated by the use of a collared design. In a Swiss National Joint Registry study of over 30,000 THAs, collared Corail™ stems had a significantly lower revision rate for aseptic loosening (0.47%) than collarless stems (0.73%; $p = 0.022$).

Perhaps most compelling is the growing body of evidence linking collared stems to reduced femoral stem subsidence—an early indicator of mechanical instability and a predictor of later aseptic loosening. A randomized controlled trial using radiostereometric analysis (RSA) found that collared stems exhibited significantly less subsidence than collarless stems at two weeks postoperatively (mean difference 2.23 mm; $p = 0.023$), although the difference diminished by one year. Additional studies using non-invasive EBRA (Ein-Bild-Röntgen-Analyse) confirm that collared stems consistently demonstrate lower average subsidence over 6 to 18 months.

Despite promising preliminary data, several gaps in the literature persist. For example, intraoperative PPFs are typically treated intraoperatively and may lead to a change in the femoral component type that is utilized. Often, this is not captured in retrospective reviews or during chart assessment even with prospectively collected data. Such arguments support the necessity of a controlled, prospective study directly comparing collared and collarless stems with standardized measurement of femoral stem subsidence and documentation of associated complications such as aseptic loosening and PPF. Furthermore, the clinical significance of early migration differences observed with various imaging modalities has not been fully elucidated, nor has their correlation with long-term outcomes been firmly established.

This proposed randomized controlled trial seeks to address these gaps by comparing the clinical and radiographic outcomes of collared versus collarless femoral stems in THA, using femoral stem subsidence as the primary endpoint and incidence rates of PPF, aseptic loosening, and PROMs as key secondary endpoints. By employing standardized radiographic measurements and robust follow-up, this study will offer high-quality evidence to inform implant selection and optimize surgical outcomes. It will also contribute to the development of clinically relevant thresholds for subsidence that can serve as early predictors of implant failure.

References:

<https://doi.org/10.1016/j.jor.2024.01.013>

MOD00024127

Page 4 of 18

4.0 Study Endpoints*

Study Endpoints

- Primary: Measurement of femoral stem subsidence at 6 weeks, 6 months, and 1-year post-operation

MOD00024127

Page 5 of 18

Revised: November 12, 2025 IRB Approved

12/18/2025 - 11/3/2026

PROTOCOL TITLE: Comparison of clinical and radiographic results of collared and collarless femoral stems in total hip arthroplasty

- Secondary: Incidence rates of periprosthetic fractures, incidence rates of aseptic loosening, and patient-reported outcome measures (PROMs)—collected in OBERD.

Safety Endpoints – N/A

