6.0 Procedures Involved*

This study is a prospective, randomized controlled trial comparing the clinical and radiographic outcomes of a collared versus collarless femoral stems of the same design in primary THA. A total of 100 participants undergoing elective, uncemented primary THA for degenerative hip disease will be enrolled.

Participants will be randomized in a 1:1 ratio to receive either a collared femoral stem or a collarless femoral stem. All patients indicated for a cementless primary total hip arthroplasty will be offered enrollment. Once consented, they will be randomized into the collared or collarless stem groups. Study participants will be informed about the risk of randomization due to removing the elements of choice from the clinician, as outlined in the informed consent form.

MOD00024127

Page 6 of 18

Revised: November 12, 2025 IRB Approved

12/18/2025 - 11/3/2026

PROTOCOL TITLE: Comparison of clinical and radiographic results of collared and collarless femoral stems in total hip arthroplasty

The primary endpoint is femoral stem subsidence, measured at postoperative 6week, 6-month, and 1-year clinical visits, which coincide with standard of care routine follow-up. Secondary endpoints include the incidence of PPF and aseptic stem loosening within the first postoperative year. Again, all research procedures are designed to align with standard perioperative and postoperative care for THA, minimizing burden for study participants. Additionally, the ACTIS Hip Stem (DePuy Synthes, Warsaw, IN) is routinely used by the participating surgeons for the last 3-4 years. The following outlines the specific protocol steps and time points:

Preoperative (Day -30 to 0):

- Obtain written informed consent either in person or via Interlace.
- Confirm eligibility criteria (inclusion/exclusion).
- Record baseline demographic data, diagnosis, and Dorr classification (from preop imaging).
- Randomization and group assignment.

Operative Day (Day 0):

- THA performed using the allocated femoral stem type (collared or collarless), via a standard surgical approach.
- Per standard practice, intraoperative documentation of any complications, including intraoperative PPFs, will be recorded by the surgical team.

Postoperative Follow-Up:

- Routine anterior-posterior (AP) pelvic and lateral hip X-rays will be obtained at 6 weeks, 6 months, and 1 year.

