 - Electronic medical records (EMR)
 - Operative reports
 - Imaging records (X-rays)
 - Clinic visit notes
- Patient-reported outcome forms—collected in OBERD, the standard platform at MedStar for collecting PROMs

Data Collected:

- Demographics and clinical variables: age, sex, BMI, comorbidities, Dorr classification.
- Operative data: stem type, surgical approach, intraoperative complications.
- Primary endpoint: femoral stem subsidence at 6 weeks, 6 months, and 1 year, measured in millimeters from standardized serial radiographs.
- Secondary endpoints:
 - PPF incidence (confirmed radiographically or operatively).
 - Aseptic loosening (evidenced by radiolucent lines, implant migration, or revision surgery).
- Other outcomes: functional scores (PROMs), adverse events, and reoperation rates.

MOD00024127

Page 8 of 18

Revised: November 12, 2025 IRB Approved

12/18/2025 - 11/3/2026

PROTOCOL TITLE: Comparison of clinical and radiographic results of collared and collarless femoral stems in total hip arthroplasty

Data Collection Methods:

- Radiographic analysis performed by independent reviewers blinded to group allocation.
- Adverse events recorded by research staff at each visit and during any interim visits.

Long-Term Follow-Up — Patients will follow standard protocol for follow-up, offering the possibility of more longitudinal reporting potentially 5-10 years postop.

Humanitarian Use Device (HUD) — N/A

This study does not involve any HUDs. All devices used (collared and collarless femoral stems) are FDA-approved for standard use in primary THA and do not require an Investigational Device Exemption (IDE). The 510(k) number for the collared hip stem is K150862 and for the collarless version is K21058.

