11.0 Vulnerable Populations* - N/A

12.0 Local Number of Subjects

For this study we aim to enroll 100 participants (50 per group) undergoing primary, cementless THA across two MedStar sites, MedStar Georgetown University Hospital and MedStar Washington Hospital Center. All participants will be screened at the time of surgical scheduling and enrolled if they meet the criteria and consent to participate. This target number of 100 participants accounts for any dropouts throughout the study. Based on our power calculation (assuming 80% power, significance of 0.05, and a SD of 0.45 mm based on prior studies), a sample size of at least 20 subjects per group (40 in total) would be needed to complete the research procedures.

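### Subsidence at three visits is the primary endpoint with no deciding visit or combining rule, while the sample size covers one comparison; the summary table also ranks subsidence as secondary

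*Protocol*

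**What the plan says.** Section 4.0 gives "Primary: Measurement of femoral stem subsidence at 6 weeks, 6 months, and 1-year post-operation". Section 6.0 repeats this twice, first as "The primary endpoint is femoral stem subsidence, measured at postoperative 6week, 6-month, and 1-year clinical visits" and then, under the data to be collected, as "Primary endpoint: femoral stem subsidence at 6 weeks, 6 months, and 1 year, measured in millimeters from standardized serial radiographs". Section 17.0 again calls subsidence at these three visits the primary outcome.

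Section 17.0 is the only place that names a test: "Differences in mean subsidence between the collared and collarless groups will be assessed using independent samples t-tests or nonparametric alternatives". It does not say at which visit.

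The sample size is given twice. Section 12.0 calculates it "assuming 80% power, significance of 0.05, and a SD of 0.45 mm based on prior studies". Section 17.0 says "A sample size of 20 participants per group (40 total) provides 80% power to detect a difference of 0.4 mm in mean stem subsidence". Neither attaches the 0.4 mm to a visit.

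On ranking, the summary table in Section 1.0 puts this in the primary-objective row: "SA1: Prospectively assess clinical outcomes in patients undergoing primary total hip arthroplasty with a collared versus collarless femoral stem of the same design". Subsidence (SA2) sits in the secondary-objective row. Sections 3.0, 4.0, 6.0 and 17.0 all make subsidence primary. Patient-reported outcomes (PROMs) are secondary in Sections 3.0 and 4.0, but Section 6.0 lists them under "Other outcomes: functional scores (PROMs), adverse events, and reoperation rates".

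**The concern.** Three visits carry primary status, yet the protocol neither states nor excludes a rule for turning three results into one conclusion. The rule affects the error rates in opposite directions. If success at any one visit is enough, three tests at 0.05 give a false-positive rate above 5%. If all three must succeed, the test becomes conservative and power falls below the stated 80% at the stated 20 per group. If the choice is made once data are available, the visit can be picked to suit the result.

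The choice could matter here. Section 3.0 cites a randomized trial in which the collared stem's advantage was significant at two weeks and had diminished by one year. Two weeks is not a visit in this trial, so it is an inference, not a stated fact, that the three planned visits may disagree.

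The Section 1.0 ranking is a separate contradiction. It does not itself change the error rate, but a reader of the summary alone would take a different outcome as primary.

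**Working it through.** **Inputs.** From Sections 12.0 and 17.0: difference 0.4 mm, SD 0.45 mm, significance level 0.05, power 80%, 20 per group. Allocation is 1:1 (Section 6.0) and planned enrolment is 50 per group (Section 12.0). The protocol does not state whether the test is one- or two-sided and gives no between-visit correlation. The correlation r is therefore assumed, equal for all pairs of visits, over the range 0 to 0.95.

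**1. Reproduce the stated sample size.** Standardized difference d = 0.4/0.45 = 0.889. Normal formula per group: n = 2 × ((z_alpha + z_power)/d)².
- Two-sided 0.05: 2 × ((1.960 + 0.842)/0.889)² = 19.9, matching the stated 20.
- One-sided 0.05: 15.6, which does not match.
- Two-sided 0.05/3 = 0.0167: 26.5, which does not match.

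The stated 20 is therefore one two-sided comparison at the full 0.05. The normal approximation gives 80.3% power at 20 per group. The noncentral t gives 78.2%, and reaches 80.3% at 21 per group.

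**2. Any-visit rule, each visit tested at 0.05.** With independent tests the false-positive rate is 1 − 0.95³ = 14.3%. For correlated tests it was found by numerical integration over equicorrelated normal statistics. The last column tests each visit at 0.0167.

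| r | Each at 0.05 | Each at 0.0167 |
|---|---|---|
| 0 | 14.3% | 4.9% |
| 0.5 | 12.5% | 4.5% |
| 0.7 | 10.9% | 3.9% |
| 0.9 | 8.4% | 3.0% |
| 0.95 | 7.3% | 2.6% |

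**3. All-three rule, each visit tested at 0.05.** Simulated t-tests, 40,000 trials per row. Power assumes the full 0.4 mm at every visit.

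| r | Power, 20 per group | Power, 50 per group | False-positive rate, 50 per group |
|---|---|---|---|
| 0 | 48% | 98% | 0.01% |
| 0.5 | 58% | 98% | 0.4% |
| 0.7 | 63% | 98% | 0.8% |
| 0.9 | 69% | 99% | 2.2% |
| 0.95 | 72% | 99% | 3.0% |

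**4. Power at one given visit (noncentral t).**

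| Completers per group | At 0.05 | At 0.0167 |
|---|---|---|
| 20 | 78.2% | 62.2% |
| 21 | 80.3% | 64.9% |
| 25 | 86.9% | 74.4% |
| 28 | 90.4% | 80.0% |
| 50 | 99.3% | 97.6% |

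**5. Ranking.** Section 1.0 has clinical outcomes primary and subsidence secondary. Sections 3.0, 4.0, 6.0 and 17.0 have subsidence primary, and the sample size is built on it. Section 2.0 lists the three aims without ranks, and its hypothesis concerns subsidence and fractures. The Section 1.0 row is the outlier.

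**The case against.** The strongest reply is that this is an omission, and that a statistical analysis plan, which is not at hand, may supply the success rule. The inflated rate arises only under an any-visit rule that the protocol never adopts, and zero correlation between serial measurements of one stem is implausible. At r between 0.7 and 0.9 the rate is 10.9% to 8.4%. At the planned 50 per group, power is high under every rule considered.

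Much of this stands, and the figures above are conditional for that reason. It does not remove the point. The protocol itself fixes the endpoint, the tests, the significance level, the difference and the sample size, and these do not fit together: three primary measurements, one comparison's worth of sample size. The choice of deciding visit is part of the endpoint's definition. A later analysis plan also cannot remove the contradiction between Section 1.0 and the rest of the protocol.

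Two further objections concern inputs.
- Sections 6.0 and 15.0 list radiographs only at 6 weeks, 6 months and 1 year. If the 6-week film serves as the reference, only two changes can be tested. The any-visit rate is then 6.5% (r = 0.95) to 9.75% (r = 0), still above 5%.
- Section 17.0 takes the 0.45 mm SD from radiostereometric studies, whereas this trial measures routine radiographs. With an assumed SD of 0.8 mm, power at 50 per group would be 70% at 0.05 and 53% at 0.0167. With an SD of 1.0 mm it would be 51% and 34%.

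Both are separate matters. They qualify the power figures and the 0.0167 option, and leave the case for one named primary test intact.

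**Conclusion.** The concern holds and should be fixed. The protocol lists three primary measurements, does not say how they decide the trial, and is sized for one unsplit two-sided comparison. An any-visit reading takes the false-positive rate from 5% to between 7.3% and 14.3%. An all-three reading takes power at 20 per group to between 72% and 48%. Both ranges rest on the assumed correlation of 0.95 down to 0, and the power range also on the protocol's SD and a 0.4 mm difference at every visit. At 50 per group and that SD, power is not the problem; the undefined success criterion is. The textual facts are certain, whereas the size of the harm depends on which rule is eventually used. The Section 1.0 ranking is a plain inconsistency with no effect of its own on the error rate.

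**What to change.** 1. In Section 1.0, make subsidence the primary objective and clinical outcomes secondary. State the rank of PROMs once and use it in Sections 3.0, 4.0 and 6.0.
2. In Sections 4.0, 6.0 (both places) and 17.0, name one visit, or one contrast from a single repeated-measures model, as the primary test at two-sided 0.05. State that the 0.4 mm applies to it, and make the other visits secondary. If a visit is named, confirm that a reference film exists for it.
3. Alternatively, keep all three visits primary at 0.0167 each and change the power statements in Sections 12.0 and 17.0 to match: 28 completers per group for 80% power at a given visit.

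The cost is wording, fixed before outcome data are seen. If 100 are enrolled, the change itself adds no patients, visits or images. Naming one test needs no correction and keeps the present calculation (21 completers per group by the t-test). The Bonferroni option raises the requirement from 21 to 28 completers per group and lowers power at 50 per group from 99.3% to 97.6%, both at SD 0.45 mm.

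One caveat: Section 26.0 speaks of enrolling at least 50 participants. If that means 50 in total, or 25 per group, one test at 0.05 has 87% power and a test at 0.0167 has 74% at a given visit. That would favour a single named test.
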